Home-based tDCS for behavioral symptoms in Alzheimer's disease and related dementias

NCT05478681

Version Date: 08/27/2024

Protocol Title: Home-based tDCS for behavioral symptoms in Alzheimer's disease and related dementias

Principal Investigator: [name], PhD, UTHealth

Co-Investigators:

[name] [name], UT Health San Antonio

[name] [name], UT Health San Antonio

[name], UTHealth

[name], UTHealth

General Information

Study Title	Home-based tDCS for behavioral symptoms in Alzheimer's disease and related dementias (ADRD)	
Short Title	tDCS for behavioral symptoms in ADRD	
Study Design	
This is an open-label, non-randomized clinical trial to assess acceptability, safety and efficacy of providing transcranial direct current stimulation (tDCS) to Alzheimer's disease and related dementia (ADRD) patients with behavioral symptoms.
 
All participants will receive active tDCS with a constant current intensity of 2mA for 30 minutes, five times per week, for six weeks. Anodal tDCS will be applied to the left dorsolateral prefrontal cortex, while cathodal electrode will be positioned on the right dorsolateral prefrontal cortex. Caregivers will set up and administer tDCS for participants with AD at home. All sessions will be remotely supervised by trained research staff through video conferencing software. Participants will be assessed at baseline, treatment day 12, treatment day 28, treatment day 42, and 6 weeks
	

	post-treatment.	
Study Participants	Patients with ADRD and behavioral symptoms will be recruited at the UTHealth Neurosciences Neurocognitive Disorders Center ([name]), and UT Physicians Center for Healthy Aging ([name]).	
Planned Sample Size	20	
Planned Study Period	12 weeks	
	Objectives	Outcome Measures
Primary Goal	To assess acceptability, and safety of providing tDCS to ADRD patients with behavioral symptoms.	Acceptability will be evaluated using Likert scale (from 0 [strongly disagree] to 10 [strongly agree]) to answer ten affirmatives regarding the use of home-based tDCS. Safety will be assessed with a questionnaire about side effects that include itching, burning, headache, fatigue, and dizziness.
Secondary Goal	To assess the efficacy of tDCS for ADRD-related symptoms, mainly behavioral symptoms.	Behavioral and cognitive symptoms will be evaluated through validated clinical instruments.

Background Information

Alzheimer's disease (AD) is the main cause of dementia and one of the great challenges of the 21st century (1). An estimated 40 million people, mostly older than 60 years, have dementia worldwide, and this number is expected to increase significantly in the next decades. Despite ongoing advances in the understanding of the pathogenesis of Alzheimer's disease and related dementias (ADRD), no treatment available can prevent or delay the cognitive decline that characterizes the condition (1). Besides cognitive impairment, nearly all patients with ADRD present behavioral and psychological symptoms, also called neuropsychiatric symptoms (NPS).

NPS have been associated with negative outcomes in ADRD, including decrease of patient and caregiver quality of life, increased risk of institutionalization, higher costs and risk of mortality (2). The term NPS is an umbrella expression that encompasses

different types of behavioral problems, including agitation, apathy, delusion, insomnia, among others (3, 4). Due to the potential complications associated with the use of psychotropic drugs (e.g. increased risk of cerebrovascular events with antipsychotics, increased risk of falls and cognitive decline with benzodiazepines) and the limited evidence of their efficacy, clinical guidelines, medical organizations and expert groups recommend non-pharmacological strategies as the first-line treatment for NPS (5, 6).

Transcranial direct current stimulation (tDCS) is a relatively novel non-pharmacological method of neuromodulation that has been studied in several neuropsychiatric conditions with promising results in depression and negative symptoms of schizophrenia (7, 8). tDCS modulates brain activity through low-intensity electrical currents applied over the scalp, and has been associated with significant changes in network connectivity involving the prefrontal cortex and the cingulate cortex, regions implicated in the neural basis of NPS (9-11).

Given the clinical relevance of NPS in ADRD, the equivocal results of the therapeutic resources available to address it, and the emerging evidence of safety and efficacy of tDCS in ADRD, our proposal aims to test the acceptability, safety and efficacy of home-based tDCS for the treatment of NPS in ADRD. Home-based tDCS circumvents critical problems observed in previous trials (16), including the need of multiple visits to medical centers for tDCS application, allowing a more intensive application (e.g. 5 x per week) for long periods.

Objectives

Objectives	Outcome Measures
Primary objective To assess acceptability and safety of providing tDCS to ADRD patients with behavioral symptoms.	Acceptability will be evaluated using Likert scale (from 0 [strongly disagree] to 10 [strongly agree]) to answer ten affirmatives regarding the use of home-based tDCS. Safety will be assessed with a questionnaire about side effects that include itching, burning, headache, fatigue, and dizziness. Acceptability scale will be applied on Week 2, 4, 6 and 12. Side effects questionnaire will be applied on Week 2, 4 and 6.
Secondary objectives To assess the efficacy of tDCS for ADRD on clinical outcomes, mainly behavioral symptoms.	Behavioral symptoms and cognitive measures evaluated through validated tools: NPI, bDAS, CSDD, MMSE. NPI will be applied on Baseline, Week 2, 4, 6 and 12, while bDAS, CSDD and MMSE will be applied on Baseline, Week 6 and Week 12.

Study Design

We will carry out an open-label study to evaluate home-based active tDCS for AD and behavioral symptoms. There will be no randomization. All eligible patients will receive exactly the same treatment. All participants (n=20) will receive active tDCS with a constant current intensity of 2mA. Anodal tDCS will be applied to the left dorsolateral prefrontal cortex, while cathodal electrode will be positioned on the right dorsolateral prefrontal cortex. Caregivers will help setting up and administering tDCS for participants with AD at home. tDCS will be applied for 30min at an intensity of 2mA, with

30 s ramping up and down.

We will target the stimulation on the dorsolateral prefrontal cortex based on the facts that prior studies showed positive results with this strategy for behavioral and cognitive symptoms of other neuropsychiatric disorders (17-19). According to previous home-based tDCS protocols (20, 21), all sessions will be remotely supervised by trained research staff (RA), therefore, the sessions will run from Monday through Friday for four consecutive weeks. The remote supervision of the sessions will be possible through video conferencing software (e.g., WebEx), and will ensure the use of proper technique and compliance to the study schedule, also monitoring any adverse events. The device (tDCS) will be programmed and cannot be tampered. Participants will be assessed at baseline, treatment day 14, treatment day 28, treatment day 42- and 6-weeks post-treatment (Fig.1). The device will be delivered to patients at baseline and will be returned at the end of the treatment (week 6).

Sample size

Following recommendations in the statistical literature analyses we will proceed using parallel frequentist and Bayesian statistical inference. Frequentist analyses will provide conventional interpretation of the relationships between predictors and outcomes: the probability of the data, given the null hypothesis. Bayesian analyses will incrementally update specified prior information regarding effects to directly yield the probability of an alternative hypothesis. Bayesian analyses will employ weakly informative priors as a default (e.g., for regression coefficients: $\sim N[\mu=0, \sigma^2=100]$). Sensitivity analyses using optimistic and pessimistic, skeptical priors will evaluate prior assumptions. Assessing the convergence of Bayesian analyses on the posterior distributions via Monte-Carlo Markov chain (MCMC) will use diagnostic evidence including effective sample size and scale reduction factors. Evaluation of posterior distributions will permit statements regarding the probability that effects of varying magnitudes exist, given the data, even with a small sample size. Frequentist analyses will evaluate all *a priori* models at the $\alpha=0.05$ (two-tailed) significance level and will employ false discovery rate (FDR) to control for Type I error across any exploratory or *post hoc* analyses. Bayesian models will be evaluated via PP threshold guidelines in the literature suggesting that PP = 75% to 90% indicates moderate evidence, PP = 91% to 96% indicates strong evidence, and PP = 97% or above indicates very strong to extreme evidence. Bayesian analyses do not conceptualize Type I error in the same way as frequentist analyses due to formally calibrating probability in the prior distribution (as opposed to long-run probabilities, as in

frequentist analyses) and are less influenced by multiple comparisons in general due to observation of the Likelihood Principle. The current Bayesian analyses stipulate posterior probabilities ≥ 0.75 (equivalent to a Bayes factor = 0.33 or 3.0) that parameter estimates are greater or less than zero provide a minimum threshold of evidence to emphasize the value in discerning effects in a small study. The Bayesian inferential paradigm can provide probabilistic estimates of effects irrespective of sample size. Power considerations focus on identifying change over time from baseline to end-of-treatment. Notably, the Bayesian analyses will provide the primary inferential results; thus considerations for the frequentist analyses are limited by the small sample size and provided solely as due diligence. Given alpha = 0.05, a sample size N = 20 provides 80% power to detect an effect size Cohen's d = 0.66.

Study Population

A maximum of 20 persons with ADRD and clinically-meaningful behavioral symptoms will be enrolled in the study. This sample size is set to maximize the number of participants that may be enrolled over the time period of the proposal assuming a credible average recruitment rate, given the financial resources.

Inclusion criteria. Participants who are 60 years or old will be considered eligible if they: (1) have ADRD and clinically-meaningful behavioral symptoms, (2) have a caregiver willing to participate in the study, (3) can speak and read English, (4) have stable doses of medications for at least one month. The diagnosis of ADRD will be verified by the investigators based on Mini-Mental Status Exam score (between 14 - 25) (22, 23). Clinically-meaningful behavioral symptoms will be determined by the Neuropsychiatric Inventory (NPI), and defined as a total score ≥ 10 arising from at least two domains (24, 25).

Exclusion criteria. Participants will be excluded if they have: (1) any unstable concurrent medical conditions, (2) history of brain surgery, seizure, or intracranial metal implantation, (3) current alcohol/substance use disorder.

Recruitment and Retention. Participants will be recruited at the *UTHealth Neurosciences Neurocognitive Disorders Center* ([name]), *UT Physicians Center for Healthy Aging* ([name]), and at the UT Health San Antonio's Glenn Biggs Institute for Alzheimer's and Neurodegenerative diseases Neurology clinic ([name]). Study flyers with summary and contact information about the study will be used at the *UTHealth Neurosciences Neurocognitive Disorders Center* as a mean to provide awareness and information to potential participants. Flyers will be available at the request of potential subjects at the moment of their visit with [name], and at dedicated spaces for research recruitment material in the *UTHealth Neurosciences Neurocognitive Disorders Center*. As serious adverse effects and problems with the device use are not anticipated, it is expected a high retention rate. The remote supervision of the tDCS or sham daily sessions by trained research staff will contribute to the retention of subjects during the trial.

Training plan. Patients will be instructed on treatment at baseline, when they will

receive the device. A trained research staff will instruct the participant's caregiver on how to handle the equipment. All sessions will be remotely supervised by trained research (RA) staff, who will be able to answer questions during the sessions and verify that the device is being used correctly.

Study Procedures

Primary Outcome

Acceptability will be evaluated using the method proposed by Ahn et al. (2019) (21). Participants and/or their caretakers will be asked to apply a Likert scale (from 0 [strongly disagree] to 10 [strongly agree]) to answer ten affirmatives regarding the use of home-based tDCS. For example, question 1: It was easy to prepare the device and accessories, question 7: I felt confident using the device. Overall acceptability across groups will be evaluated by descriptive measures of satisfaction ratings. We expect that participant satisfaction ratings at the end of treatment will demonstrate high acceptance of tDCS treatment in the present sample. Acceptability scale will be applied on Week 2, 4, 6 and 12.

Safety will be assessed with a questionnaire about side effects that include itching, burning, headache, fatigue, and dizziness (21). The most common side effects of tDCS reported in the literature are very mild and include tingling, burning sensation, and skin redness, while other less common side effects may include headache, sleepiness, dizziness, and difficulty concentrating (22-23). Although rare, a possible adverse event of tDCS is the occurrence of skin lesions or small skin burns on the site where electrodes touch the skin (24-25). The side effects questionnaire will be applied on Week 2, 4 and 6 to assess the incidence and frequency of side effects in our recruited sample. We expect that the occurrence of side effects will be similar to the frequencies reported in the scientific literature, demonstrating that home-based tDCS is a safe and feasible intervention to be used on the management of ADRD patients with behavioral symptoms.

Secondary Outcome

The main efficacy measure will be change on the Neuropsychiatric Inventory (NPI) score (26), the best-validated tool for measuring NPS in dementia patients. This 12-item informant-based interview is a widely accepted measure of NPS in dementia. The NPI consists of a detailed evaluation of the following 12 neuropsychiatric domains: hallucinations, delusions, agitation/aggression, depression, anxiety, irritability, disinhibition, euphoria, apathy, aberrant motor behavior, change in night-time sleep behavior, and changes in appetite and eating (27). Each NPS domain is rated according to its severity (0-3) and frequency (0-4) (28). NPS will be assessed at baseline, during treatment (weeks 2, 4 and 6) and 6 weeks post-treatment. Our hypothesis is that patients receiving tDCS will demonstrate lower NPI scores at the end of treatment.

Other clinical outcome measures will include: (1) total score on the Brief Dimensional Apathy Scale (bDAS) (29); (2) depressive symptoms as assessed by the

Cornell Scale for Depression in Dementia (CSDD) (30); (3) cognition as evaluated by the Mini-Mental State Examination (MMSE), which includes memory, language, praxis and orientation tasks, yielding a global cognition score ranging 0 to 30, with higher scores indicating better performance (31). Our hypothesis is that all participants receiving treatment will demonstrate lower scores on the bDAS and CSDD, and higher scores on the MMSE at the end of treatment.

NPI will be applied on Baseline, Week 2, 4, 6 and 12, while bDAS, CSDD and MMSE will be applied on Baseline, Week 6 and Week 12.

Sociodemographic and Clinical (health history, use of medication and life habits) *data* (gender, age, marital status and education) will be collected at the baseline.

Assessment	Baseline	Week 2	Week 4	Week 6	Week 12
Medical History Questionnaire	X				
MMSE (Secondary outcome)	X			X	X
NPI (Secondary outcome)	X	X	X	X	X
bDAS (Secondary outcome)	X			X	X
CSDD (Secondary outcome)	X			X	X
tDCS experience questionnaire (Primary outcome)		X	X	X	X
Side effects questionnaire (Primary outcome)		X	X	X	

Table 1. Timetable for Collection of Data

Data and Safety Monitoring

Data will be collected from 20 human participants, and all information will be de-identified in order to protect their confidentiality. All clinical information will be stored in dedicated files at UT Health Department of Psychiatry and Behavioral Sciences. The data generated in this project will be presented at national or international conferences and published in a timely fashion.

Statistics

Statistical modeling will primarily use generalized linear modeling (GLM) with multilevel components (GLMM) for correlated observations. Potentially nonlinear relationships between predictors and outcomes will be evaluated via inclusion of polynomial or spline effects. Continuous, dichotomous, and count-distributed data will utilize linear, logistic, and Poisson/negative binomial regression, respectively (each with a canonical link function). Evaluation of distributional assumptions will use residual plots, formal statistical tests, and posterior predictive checking. Violations of assumptions will be addressed via transformation, robust estimation, stratification, and/or coefficient scaling

where appropriate. Statistical analyses will be performed using the R statistical computing environment via packages lme, rstan, and brms.

Ethics/Protection of Patient Confidentiality

The sample of this study consists of 20 older adults aged 60 years-old and over with ADRD and behavioral symptoms. Study participants or their legally authorized representatives will give informed consent. Moreover, caregivers and/or relatives will be required to be present during the clinical assessments and tDCS sessions to ensure reliable information and proper use of the device. Participants will be recruited without any specific regard to sex, race, religion or ethnicity. Patients will be recruited at the UTHealth Neurosciences Neurocognitive Disorders Center, and UTHealth Center for Healthy Aging. We will recruit ADRD patients whose dementia is of mild to moderate severity. Adults younger than 60, adolescents and children are excluded as we are focusing on dementia, an age-related disorder that usually affects individuals aged 60 and older. No other special classes of vulnerable individuals will be included. It is anticipated that the subject demographic profile will mirror the larger population of individuals with ADRD from which they are recruited.

Informed Consent and Assent. Potential subjects and their caregivers/relatives will be informed about the study purpose, procedures, risks and benefits. They will be informed that participation in the research study is voluntary and that they are free to decline to be in the study, or to withdraw from it at any point. Study records will be kept confidential. Study information will be coded, and only study personnel will have access to the files.

Protection Against Potential Risks. The risks to the subjects involved in this study are minimal. To ensure this, we will take necessary steps to reduce risk for all study participants. We will try to create an atmosphere of security and trust prior any clinical assessment in order to minimize any discomfort with the research questions. In addition, subjects are always given permission to not answer questions with which they feel uncomfortable. A number of procedures (e.g. use of identifying numbers instead of names) will be implemented to protect subjects against loss of confidentiality. Side effects related to active tDCS application are uncommon, and mild when present, including: itching and burning sensation on the scalp, mild headache, dizziness, and fatigue. Although rare, a possible adverse event of tDCS is the occurrence of skin lesions or small skin burns on the site where electrodes touch the skin (24-25).

Potential Benefits to Research Participants. If our hypothesis is correct, all subjects might benefit from the study participation. Importantly, the results will be relevant to the field of AD and neuromodulation.

Significance

Our proposal will address a frequent and sometimes overlooked clinical problem in patients with ADRD, i.e. behavioral symptoms. The proposal can advance the field of non-pharmacological strategies for NPS, also presenting a great potential for clinical translation. Home-based intervention with real-time monitoring through a secure conferencing platform is a new modality for improving symptom management in ADRD. Moreover, home-based, remotely supervised tDCS has advantages over clinic-based sessions, considering the time and cost associated with attending multiple sessions over several days. Caregivers will be trained at the in-person baseline visit, and all the tDCS sessions will be remotely supervised via secure videoconferencing software by trained research staff for the entire duration of each session to ensure the use of proper technique and to monitor any adverse events.

Costs and Compensations

Participants will not be charged for tests, procedures or other costs incurred solely for the purposes of this research. Patients will receive a voucher of US 50.00 for their time dedicated to each evaluation (total number of assessments = 5).

Publication Plan

This study will represent an original contribution to the areas of non-pharmacological approaches for NPS in ADRD and neuromodulation. The results will be presented in national and international meetings, and published as a research manuscript.

References

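### Side effects still present at Week 6, or first noticed afterwards, have no later scheduled safety assessment, although a Week 12 visit already takes place

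*Combined protocol and SAP*

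**What the plan says.** The primary objective is "To assess acceptability and safety of providing tDCS to ADRD patients with behavioral symptoms". The Objectives table sets the two primary measures on different schedules: "Acceptability scale will be applied on Week 2, 4, 6 and 12", but "Side effects questionnaire will be applied on Week 2, 4 and 6". The safety paragraph under Study Procedures, Primary Outcome, repeats the three time points and gives the purpose as the incidence and frequency of side effects. In Table 1 the row "Side effects questionnaire (Primary outcome") carries three marks, for Weeks 2, 4 and 6, and is blank at Week 12.

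The listed items include itching, burning, headache, fatigue and dizziness. The same safety paragraph names, as a rare adverse event, "the occurrence of skin lesions or small skin burns on the site where electrodes touch the skin".

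Study Design says that the device "will be returned at the end of the treatment (week 6"), and the last visit is six weeks post-treatment. All sessions are supervised by video, and that supervision is also meant to pick up adverse events (Study Design; Significance). The section headed Data and Safety Monitoring deals with de-identification, storage and dissemination. It describes no adverse-event follow-up or reporting window.

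**The concern.** Five of the six outcome instruments are repeated at Week 12. The one that is not is the safety instrument, which is primary. The reason cannot be a missing contact, because the visit exists and is one of the five compensated assessments. The documents give no reason for the difference.

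Two kinds of event fall outside the schedule: an effect recorded at Week 6 whose outcome is never asked about, and an effect first noticed after the Week 6 form. A skin lesion or small burn is the clearest example. The paper could then report whether benefit lasts to Week 12 next to a safety statement that stops at Week 6. The protocol expects its results to show that home-based tDCS is safe, and a reader would reasonably want to know whether effects present at the last form cleared.

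**Working it through.** **Inputs.** Instrument schedules come from the Objectives table, Study Procedures and Table 1. The 12-week study period, N = 20 and five sessions a week for six weeks come from General Information. The conflicting statement of four consecutive weeks and the Week 6 device return come from Study Design.

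**Step 1: scheduled assessments after Week 6.**

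| Instrument | Role | Scheduled at | After Week 6 |
|---|---|---|---|
| Side-effects questionnaire | Primary | Weeks 2, 4, 6 | 0 of 3 |
| Acceptability form | Primary | Weeks 2, 4, 6, 12 | 1 of 4 |
| NPI | Secondary | Baseline, Weeks 2, 4, 6, 12 | 1 of 5 |
| bDAS, CSDD, MMSE | Secondary | Baseline, Weeks 6, 12 | 1 of 3 each |

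The three places that state the side-effects schedule agree, so this is the plan's intent and not a slip in one of them.

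**Step 2: other sources of safety information.** On the six-week schedule, supervised sessions give up to 5 × 6 = 30 monitored contacts per patient, and all of them end when treatment ends. The NPI, CSDD and MMSE at Week 12 might show behavioral or cognitive worsening, but they are efficacy outcomes and do not ask about side effects. Spontaneous reports are possible, but no procedure for recording them is described. Scheduled safety readings after Week 6 therefore number 0.

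**Step 3: length of the gap.** 12 − 6 = 6 weeks, which is 6/12 = 50% of calendar time. On the six-week schedule no stimulation is given in those weeks, so the 50% is not a share of exposure or of risk.

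**Step 4: dependence on the session schedule.**
- Six weeks of sessions: the Week 6 form is the end-of-treatment reading, and no safety form is given off treatment.
- Four weeks of sessions: the Week 6 form falls 6 − 4 = 2 weeks after the last session, so one post-treatment reading exists. Weeks 6 to 12 still have none.

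**Step 5: what a Week 12 form would add.** Planned side-effects forms rise from 20 × 3 = 60 to 20 × 4 = 80. If n patients complete it and none reports a persistent or late effect, the exact one-sided 95% upper bound p solves (1 − p)^n = 0.05, so p = 1 − 0.05^(1/n):
- n = 20: 1 − 0.05^(1/20) = 13.9%
- n = 18: 15.3%
- n = 16: 17.1%

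The completer numbers 18 and 16 are assumptions. Under the present schedule no such bound can be given.

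**Step 6: power.** The plan's only power figure (N = 20, d = 0.66, two-sided alpha 0.05, 80%) is reproduced by a paired t-test with 19 degrees of freedom: 79.9%. It concerns change from baseline to end of treatment, and neither the gap nor the fix alters it.

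**The case against.** The strongest defense is that the form does what it is meant to do: "The side effects questionnaire will be applied on Week 2, 4 and 6 to assess the incidence and frequency of side effects in our recruited" patients. No goal of duration, resolution or late onset is set, and stopping an incidence form when exposure stops is defensible in a 20-patient open-label study. Up to 30 live-supervised sessions add to it. This stands, and it confines the point to what happens after Week 6.

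A reader might infer that the trial cannot show whether side effects resolve, or that half of the safety data are missing. The documents support neither. An effect reported at Week 2 or 4 can be seen to have gone by Week 6, provided each form asks about the period since the one before; the recall period is not stated. The 50% is calendar time only.

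Three further objections have force:
- The documents call the expected effects mild and skin lesions rare, and give no rate or timing for persistent or delayed effects. The likely yield is therefore unknown, though mildness is an expectation that this trial is meant to test.
- Skin lesions are not among the listed questionnaire items. The list may not be exhaustive, but repeating it unchanged might miss the event that matters most here.
- Headache, fatigue and dizziness are non-specific. With no control arm and no baseline side-effects form, a Week 12 report could not readily be attributed to tDCS.

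The last two objections shape the remedy. They do not remove the gap.

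A reader might also conclude that the Week 12 acceptability form should make way, since the device has been returned by then. That would remove a scheduled primary-outcome assessment to save a few minutes, and it is unnecessary.

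**Conclusion.** The point holds in a limited form. Effects present at Week 6 have no later scheduled safety reading, and effects first noticed afterwards have none at all, although a visit that could supply one already takes place. The size is 0 scheduled safety readings over 6 calendar weeks, against one Week 12 reading for each of the other five outcome instruments. On-treatment incidence remains estimable, and sample size, power and the efficacy analyses are untouched.

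This is a cheap improvement to a primary objective, not a defect that invalidates it. Saying that no safety form is given off treatment assumes the six-week session schedule; on the four-week statement, Week 6 is itself a post-treatment reading. The absence of any scheduled assessment after Week 6 holds under both. The conclusion also assumes that no adverse-event follow-up is laid down outside these documents.

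**What to change.** Add the side-effects questionnaire to the Week 12 visit in the Objectives table, in the safety paragraph of Study Procedures and in Table 1. At that visit it should ask:
- which effects present at Week 6 have not resolved;
- which effects were first noticed after Week 6;
- explicitly, whether there is or has been a skin lesion or burn at an electrode site, and when it was first noticed.

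Report on-treatment incidence (Weeks 2, 4 and 6) and Week 12 persistence or late onset as separate descriptive results. State the number who completed the Week 12 form, and say that the Week 12 figures carry no causal attribution because there is no control arm and no baseline side-effects form. Keep the Week 12 acceptability form.

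Reconcile the four-week statement in Study Design with the six-week statement in General Information, and then label the Week 6 form as on-treatment or post-treatment accordingly.

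The cost is a small amendment, at most 20 additional short forms and a few minutes per patient at a visit that is already compensated. No sample-size or power recalculation is needed.
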